4.3.7 Peer-Educators – training and responsibility

The PEs for this research project will be recruited within the existing network of Sentebale (www.sentebale.org). The Sentebale PEs are young people (18-24 years) living in a community from their attached health facility catchment area. All Sentebale PEs received at the beginning of their volunteering work a one-week training on general issues around HIV/AIDS and youth-related health topics with focus on psychosocial support. All PEs involved in PEBRA study will receive an additional training on the PEBRAApp, the use of the tablet, reporting & documentation system, obtaining of informed consents and other study-specific procedures.

4.3.8 Blinding

This is a pragmatic implementation trial, assessing the effectiveness of a new DSD model. Due to the nature of the trial it is not possible to fully blind participants nor staff to the intervention. But allocation will be concealed due to the design of a cluster randomization, which implies randomization before participant inclusion.

5 ENDPOINTS AND DEFINITIONS

Table 1 summarizes all endpoints.

5.1 Primary endpoint

In care with documented viral suppression at 12 months, defined as the proportion of participants in care with a documented VL <20 copies/mL 12 months (range: 9 – 15 months) after enrolment out of all participants enrolled

- i. *Rational for VL suppression level at 20 copies/mL: VL determination will be done on COBAS TaqMan® HIV-1 Test, v2.0 (Roche Diagnostics) using plasma, and has a reliable lower limit of detection of 20 copies/mL*
- ii. *Definition of "in care": at least one ART visit in the defined window*
 - I. *Including participants who transferred out to any other health facility with known outcome (documented proof of follow-up visit or laboratory test)*
 - II. *Excluding participants who died (all-cause), were lost to follow-up (LT FU), or were known defaulters/refusers, i.e. were more than 2 months late for ART refill with a reason available (e.g. currently no money for clinic-visit, busy working in South Africa, etc.)*
- iii. *The study will use VL results from routine VL monitoring. To synchronize routine VL monitoring and study VL monitoring, study staff will help ensure each site has the capacity to collect these samples and will support existing systems that help to provide results back to sites. VLs will only be performed on individuals who return for visits and no tracking will be performed by the study staff to obtain VLs.*

5.2 Secondary endpoints

- a) Adherence to ART at 3 months (range 2.5 – 3.5), 6 months (range 5 – 8) and 12 months (range 9 – 15) after enrolment
 - i. *Assessed by 4 different setting- and age-validated ART adherence questions²⁰⁻²²:*
 - a. *pill count: change in percentage*
 - b. *"When was the last time you missed any medications?" [i) past week, ii) 1-2 weeks ago, iii) 3-4 weeks ago, iv) never]: Dichotomous outcome missed doses vs. no missed doses in the past month*
 - c. *"ART missed at two or more consecutive days within last month?" ("drug holiday" question)*
 - d. *"How would you rate your adherence over the last month" [i) very poor, ii) poor, iii) fair, iv) good, v) very good, vi) excellent]: Dichotomous outcome adherent vs non-adherent (anything less than 'excellent')*
- b) Quality of Life (QoL) at 6 months (range 5 – 8) and 12 months (range 9 – 15) after enrolment
 - i. *Assessed by WHO QoL in PLHIV: WHO HIV QoL questionnaire (whoqol_hiv_bref questionnaire with 31 five-point Likert Scale items with categorical outcome)²³⁻²⁵*
- c) Perceived quality of ART Care (QoC) / patient service satisfaction at 6 months (range 5 – 8) and 12 months (range 9 – 15) after enrolment
 - i. *Assessed by a setting-validated QoC and patient service satisfaction questionnaire (12 five-point Likert Scale items with categorical outcome)²⁶ by an external data collector, not the PE*

- d) Engagement in care at 6 months, defined as the proportion of participants engaged in care 6 months (range 5 – 8) after enrolment out of all participants enrolled
 - i. *Definition of “in care”: at least one ART visit in the defined window*
 - I. *Including participants who transferred out to any other health facility with known outcome (documented proof of follow-up visit or laboratory test)*
 - II. *Excluding participants who died (all-cause), were lost to follow-up (LTFU), or were known defaulters/refusers, i.e. were more than 2 months late for ART refill with a reason available (e.g. currently no money for clinic-visit, busy working in South Africa, etc.)*
- e) Alternative viral suppression at 12 months, defined as the proportion of participants with a documented VL <1000 copies/mL 12 months (range 9 – 15) after enrolment out of all participants enrolled
 - i. *Rational for alternative VL suppression definition at 1000 copies/mL: According to the currently used Lesotho national guidelines, an unsuppressed VL is defined as a 1000 copies/mL or more*
- f) Engagement in care at 12 months, defined as the proportion of participants engaged in care 12 months (range 9 – 15) after enrolment out of all participants enrolled (definitions see above under d)
- g) All-cause mortality at 6 and 12 months, defined as the proportion of participants dead 6 months (range 5 – 8) and 12 months (range 9 – 15) after enrolment, respectively, out of all participants enrolled
 - i. *Verbal autopsy to capture cause of death whenever possible. No death certificate or autopsy report required.*
- h) LTFU at 6 and 12 months, defined as the proportion of participants LTFU 6 months (range 5 – 8) and 12 months (range 9 – 15) after enrolment, respectively, out of all participants enrolled
 - i. *We define participants lost to follow-up if they or their treatment buddies were more than 2 months late for a scheduled consultation or medication pick-up and no information was found about the participant*
- i) Transfer out at 6 and 12 months, defined as the proportion of participants who transferred out to any other health facility (than the initially attached one) with known outcome (documented proof of follow-up visit or laboratory test) 6 months (range 5 – 8) and 12 months (range 9 – 15) after enrolment, respectively, out of all participants enrolled

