5.3 Safety Endpoint

We specifically assess the safety of our PEBRA model, defined as the proportion of participants experiencing a Serious Adverse Events (SAE) within 12 months after enrolment out of all participants enrolled. See chapter [12.4](#) for a detailed description of SAEs.

TABLE 1. Summary of PEBRA study endpoints

endpoints	Following enrolment		
	At 3 months (range: 2-5 – 3.5)	At 6 months (range: 5-8)	At 12 months (range: 9-15)
In care with documented viral suppression <20 copies/ml			Primary
Adherence to ART	Secondary	Secondary	Secondary
QoL	Secondary	Secondary	Secondary
QoC	Secondary	Secondary	Secondary
In care with documented viral suppression <1000 copies/ml			Secondary
Engagement in care		Secondary	Secondary
All-cause mortality		Secondary	Secondary
LTFU		Secondary	Secondary
Transfer out		Secondary	Secondary
SAE			Safety

Note: we consider 1 month = 30 days

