11.2 Analyses

All analyses will be done using R (the R Foundation for Statistical Computing) or Stata (version 14, Stata Corporation) in Lesotho. For all tests, we will use 2-sided p-values with alpha 0.05 level of significance. A detailed data analysis plan will be developed separately.

Clusters will be set as unit of randomization (stratified by district), whereas individuals are set as unit of analysis. Multilevel random effects models will be used to analyze the data. We will present a CONSORT flowchart of the participants, including screening, enrollment and follow-up. The following analysis sets will be used in this trial:

1. Intention-to-treat (ITT) set: All study participants will be evaluated according to cluster assignment at randomization
2. Per-protocol (PP) set: This set includes all participants who completed the study without a major protocol deviation

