18.3 Case Report Form

We refer to attached document, called “PEBRA study_CRF/Codebook”

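### The missed-dose adherence item, as printed, offers no answer for a last miss more than 4 weeks ago, so some participants adherent in the past month may be misclassified or missing

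*Combined protocol and SAP*

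**What the plan says.** Section 5.2 a) describes adherence as "Assessed by 4 different setting- and age-validated ART adherence questions", at 3, 6 and 12 months. Item (b) of that list asks "When was the last time you missed any medications", with no recall limit in the question. The printed answers are "i) past week, ii) 1-2 weeks ago, iii) 3-4 weeks ago, iv) never", and the derived variable is "Dichotomous outcome missed doses vs. no missed doses in the past month".

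Section 5.2 does not say which answers fall in which class. The first three all lie within the past month, so by implication they mean a miss, and *never* alone means no miss. Items (c) and (d) of the same list do carry a one-month recall period in their wording; item (b) does not.

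The note under Table 1 in section 5.3 fixes the length of a month: "Note: we consider 1 month = 30 days".

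Fuller coding could be in two places that are not part of the reviewed text: the CRF/codebook, which section 18.3 lists as an attachment, and the analysis plan, of which section 11.2 says "A detailed data analysis plan will be developed separately".

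**The concern.** The question looks back without limit, the outcome is cut at one month, and the answers stop at 4 weeks and then jump to *never*. Someone whose last miss was six weeks ago belongs in the no-miss class but has no true answer that leads there.

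If *never* is taken literally, a truthful participant who missed a dose before enrolment cannot be classed as adherent on this item at any later visit, however good the adherence since. The item would then be poor at registering the improvement that the intervention aims for. If the item is fielded as printed, the problem cannot be undone in the analysis: people whose last miss was over a month ago and people whose last miss really was 3-4 weeks ago would share one code.

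**Working it through.** There is no stated figure to reproduce; the question is which answers exist and how they are scored.

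**Step 1. Coverage.** Inputs: the four printed options (5.2 a), read literally as days 0-7, 7-14, 21-28 and *never*; a month of 30 days (note to Table 1). Days since last miss with no matching option: 15-20, and every day from 29 onward.

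**Step 2. Effect on the binary outcome.**

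| Last miss | True class | Available answers | Resulting class |
|---|---|---|---|
| Days 15-20 | Miss | *1-2 weeks ago* or *3-4 weeks ago* | Miss: correct either way |
| Days 29-30 | Miss | *3-4 weeks ago* | Miss: correct |
| Days 29-30 | Miss | *never* | No miss: wrong |
| Beyond day 30 | No miss | *never* | No miss: correct, though the answer is untrue |
| Beyond day 30 | No miss | *3-4 weeks ago* | Miss: wrong |
| Any of these | As above | Left blank | Missing |

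The gap at 2-3 weeks therefore does not change the outcome unless the answer is skipped. If the options are meant as whole weeks (1 or 2; 3 or 4), that gap largely disappears. The gap beyond 4 weeks does matter.

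**Step 3. Size.** Let g be the share of all participants whose last miss was more than 30 days ago, and q the share of those who answer *3-4 weeks ago*. The share of all participants wrongly classed as having missed is g x q. The documents give neither input, so both are assumptions:

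| g | q = 0 | q = 0.25 | q = 0.5 | q = 1 |
|---|---|---|---|---|
| 5% | 0% | 1.3% | 2.5% | 5% |
| 10% | 0% | 2.5% | 5% | 10% |
| 20% | 0% | 5% | 10% | 20% |
| 40% | 0% | 10% | 20% | 40% |

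**Step 4. After the fix.** With an option for more than 30 days ago, scored as no miss, these participants have a true answer in the right class, and g x q from this source falls to 0. A cut at 4 weeks would not do this fully: days 29-30 lie inside the protocol's 30-day month and would be scored as no miss.

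**The case against.** The strongest defence is that *never* is meant as never within the recall window. The derived variable in the same line refers to the past month, and anyone beyond day 30 who answers that way is classed correctly. On that reading q is near zero and little is lost. This stands as a possibility and is why the range starts at 0, but the printed question does not state a window, so respondents and interviewers must supply one.

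Second, the fielded form and the detailed analysis plan are not visible, and the item is attributed to validated instruments. The form may already hold the missing option. That also stands: the point concerns the item as printed, and checking the form comes first.

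Third, the impact is limited. Pill count and the two items with one-month recall are separate measures, and section 11.2.2 reports binary secondary endpoints as between-arm odds ratios from items worded alike in both arms. This stands in the main. Equal wording does not guarantee equal q, because the trial is open-label (4.3.8) and peer educators collect data on the tablets (12.1), but nothing in the documents shows that q would differ by arm.

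A reader might infer more than the text supports:

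- **That the 2-3 week gap also corrupts the outcome.** It does not, since both neighbouring answers score as a miss.
- **That the outcome cannot be derived at all.** It can, for everyone whose answer falls in the right class, including those beyond day 30 who say *never*.
- **That many participants are affected.** Random misses with a mean gap m of 30, 60 or 90 days would put the last miss beyond 28 days with probability exp(-28/m) = 39%, 63% or 73%. That describes hypothetical occasional missers, not all participants, and the model and its gaps are invented. It also leaves q unknown, so the misclassified share of that subgroup still starts at 0.

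**Conclusion.** The point holds in limited form. As printed, the item lacks an answer for a last miss more than 4 weeks ago and has no scoring rule, so participants who were adherent in the past month but missed earlier may be misclassified or missing. The size is g x q of all participants: with g assumed at 5% to 40%, from 0-5% up to 0-40%, depending on how respondents resolve the ambiguity. It cannot be narrowed from the documents, and zero is not excluded. The 2-3 week gap is a wording flaw only.

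The consequence is confined to one of four measures within one secondary endpoint, mainly its absolute rates, with possible dilution of the contrast between arms. The primary endpoint and the sample size are untouched. The change is worth making because it is cheap before recruitment and the lost distinction could not be recovered later. The conclusion assumes that the tablet form follows the printed list.

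**What to change.** Before the main trial, compare the printed options with the CRF/codebook and the cited instrument. If the form already has the missing option, only section 5.2 needs aligning. If not:

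1. Make the options contiguous and complete: past week; 1-2 weeks ago; more than 2 weeks and up to 30 days ago; more than 30 days ago; never.
2. State in section 5.2 that the last two count as no miss in the past month and the first three as a miss. Setting the cut at 30 days matches the note to Table 1.
3. Change the protocol line and the tablet form together, so that baseline and follow-up use the same item.

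The cost is an edit to the tablet form and one protocol line, with no extra visit or procedure. The timeline in section 16 already allows for a protocol amendment between the pilot and the main trial. The downside is a possible departure from the wording of the cited item, which should be noted if it occurs.

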4.3.4 Procedures in all study clusters

A trained PE per cluster will actively screen all AYPLHIV for eligibility. If eligible, the PE will continue with the baseline assessment, using a tablet-based application. The following data will be collected (from medical records and patient interview):

- Consent documentation (and if not consenting, then reason for refusal and stop data collection)
 - Details about consent process see in section 13.1
- ART number
- Clinic/Cluster
- Year of birth
- Gender
- Village
- Cellphone number
- Date of ART initiation
- WHO-stage at ART initiation
- Laboratory information: CD4 at ART initiation, last CD4, VL history and baseline VL*
- Co-morbidities
- TB history
- Co-medication
- ART regimen history
- Socio-demographic data including age, gender, level of education, employment status, marital status, pregnancy
- Structural data incl. distance and time and costs (incl. opportunity costs) to visit the health facility
- HIV/AIDS knowledge and stigma¹⁹
- Adherence: Pill count and setting- & age-validated treatment adherence questions²⁰⁻²²
- Quality of Life (QoL): WHO HIV QoL questionnaire (whoqol_hiv_bref questionnaire)²³⁻²⁵
- Quality of Care (QoC): a setting-validated perceived QoC & patient satisfaction questionnaire²⁶

*Note: Baseline VL is defined as the last VL within the previous 12 months, taken from the medical records (bukana, patient file, laboratory databases). If no VL within previous 12 months available, then the participant will be sent to the nurse for blood draw for routine VL measurement. This is not a study-specific procedure, but standard of care. If the patient is new in care and due for 6 months VL, then the 6m routine VL will be taken as baseline VL.

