12 DATA MANAGEMENT, BIOLOGIC MATERIAL, MONITORING, SAE

12.1 Data entry, data monitoring, data storage, data confidentiality

The PEs collect data directly in two tablet-based applications: PEBrApp (patient management tool and data collection tool) and KoboToolbox (data collection tool, incorporated in PEBrApp). The PEBrApp is password-protected and only accessible to the peer-educator that is responsible for the participant. All data will be regularly uploaded into a password-protected database. Similarly, relevant data for the SMS intervention will be entered and stored in a separate encrypted and password-protected online database, that offers the possibility to send out SMS automatically and is connected to the district laboratory database containing the VL results (VL platform, www.lstowards909090.org/db). The VL platform data are stored on a dedicated server in a data center, which meets FINMA-RS 08/07 requirements, is ISO-27001-certified, encrypts data in-transit with SSL and all patient names at-rest using OpenSSL with AES-256-CTR cipher method. SMS are dispatched using the trusted third-party provider Twilio, certified with the Privacy Shield Framework. Access to all data collection tools and databases are strictly limited and regulated through personal user profiles.

Data for the follow-up period comes from routinely collected medical records at the health facilities, primarily from the patient file, if necessary also from patients health booklet (bukana), antenatal care register, postnatal care register, ART register, ART treatment card and file, TB treatment register, TB treatment card, pharmacy register/dispensing logs, and the viral load monitoring platform. All the above mentioned documents act as source documents. For additional information that is not part of these documents, data is taken specifically for the study and the two data collection tools act as source document.

Following an initial period of weekly quality review, a study data manager will monitor data quality and completeness on a bi-monthly/monthly basis. Queries about the data will be sent to the local team for follow-up and correction, as needed. Data integrity checks will be written into the data collection tools to limit the entry of incorrect data and ensure entry of data into required fields.

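### Follow-up quality of care is kept away from the peer educator, but adherence and quality of life are given no such safeguard, so their arm comparisons are open to differential reporting

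*Combined protocol and SAP*

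**What the plan says.** All references are to the combined protocol and SAP.

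- **QoC (5.2c).** The 12-item questionnaire at 6 and 12 months is to be administered "by an external data collector, not the PE".
- **Adherence (5.2a).** "Assessed by 4 different setting- and age-validated ART adherence questions", at 3, 6 and 12 months. One of the four is a pill count. The other three are self-report, including "How would you rate your adherence over the last month", where only the top of six ratings counts as adherent. No collector is named.
- **QoL (5.2b).** "Assessed by WHO QoL in PLHIV: WHO HIV QoL questionnaire", 31 items at 6 and 12 months. No collector is named.
- **Baseline (4.3.4), all clusters.** "If eligible, the PE will continue with the baseline assessment, using a tablet-based application". The baseline list includes adherence, QoL and QoC.
- **Data collection (12.1).** "The PEs collect data directly in two tablet-based applications". PEBRApp is "only accessible to the peer-educator that is responsible for the participant". Follow-up data come mainly from routine records; for what those records do not hold, "data is taken specifically for the study and the two data collection tools act as source document".
- **Roles (4.3.5, 4.3.6, 4.3.8).** In intervention clusters the PE coordinates refills, repeats the preference assessment every one or three months and may provide support by phone or home visit. In control clusters the nurse coordinates refills. Full blinding of participants or staff is stated to be impossible.

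**The concern.** By excluding the PE from follow-up QoC, the plan treats the PE as unsuitable for collecting one patient-reported comparison. The same reasoning applies to the two neighbouring endpoints, which have no matching safeguard. If the PE asks these questions, an intervention participant reports missed doses or poor wellbeing to the person who arranges his or her treatment and support. A control participant reports them to a PE who does not coordinate the refills. Answers may then differ between arms for reasons unrelated to actual adherence or wellbeing.

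At stake is the interpretation of the self-reported adherence results and of QoL. Section 11.2 plans no sensitivity analysis for reporting bias, and no model fitted afterwards can separate a reporting difference from a true effect. Drug levels, which could check adherence objectively, are only a possibility and only at 12 months (section 6).

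**Working it through.** **Step 1. Who collects what at follow-up**

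| Endpoint | Collector named in 5.2 | What other sections imply |
|---|---|---|
| QoC, 6 and 12 months | External collector, PE excluded | – |
| Self-reported adherence, 3, 6 and 12 months | None | PE: asks the items at baseline (4.3.4) and is the stated user of the study tools (12.1) |
| QoL, 6 and 12 months | None | PE, for the same reasons |
| Pill count | None | Not self-report, although the person counting is not named |
| Primary endpoint | Not applicable | Laboratory viral load and care records (5.1) |

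No section provides another interviewer, self-completion or a blinded assessor for adherence or QoL. PE collection at follow-up is thus an inference from 4.3.4 and 12.1, not a statement in 5.2.

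**Step 2. Reproduce the plan's own figure, to check the method**

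Inputs from 11.1 and 11.2: 300 participants, 20 clusters, 15 per cluster, ICC 0.05, control rate 70%, a 20% increase read as 70% versus 90%, two-sided alpha 0.05.

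- Design effect = 1 + (15 − 1) × 0.05 = 1.70.
- SE = √[1.7 × (0.70 × 0.30 + 0.90 × 0.10) / 150] = √(1.7 × 0.30 / 150) = 0.0583.
- Noncentrality = 0.20 / 0.0583 = 3.43.
- Power from the noncentral t with 20 − 2 = 18 df (critical value 2.101) = 0.900.

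This matches the stated 90%.

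**Step 3. Illustrate a reporting difference by the same method**

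Assumptions not in the documents: one binary adherence item, no true effect, control rate p between 50% and 70%, and excess over-reporting of s points in the intervention arm. The design effect of 1.7 is carried over from the primary endpoint.

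SE = √{1.7 × [p(1 − p) + (p + s)(1 − p − s)] / 150}; noncentrality = s / SE; two-sided rejection from the noncentral t on 18 df.

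Example, p = 0.50 and s = 0.10: SE = √[1.7 × (0.25 + 0.24) / 150] = 0.0745; noncentrality = 1.34; rejection = 24.6%.

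| Excess over-reporting | Rejection, p = 50% | Rejection, p = 70% | Spurious odds ratio, p = 50% to 70% |
|---|---|---|---|
| 3 points | 6.7% | 7.0% | 1.13 to 1.16 |
| 5 points | 9.7% | 10.9% | 1.22 to 1.29 |
| 10 points | 24.6% | 31.0% | 1.50 to 1.71 |
| 15 points | 48.8% | 63.1% | 1.86 to 2.43 |

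Without a reporting difference the rejection rate is 5%. No figure is computed for QoL, because the documents give no distribution for it.

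**The case against.** Several objections limit how far the point can be taken.

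- **The collector is inferred.** A reader might take it as settled that the PE asks these questions at follow-up. Section 5.2 does not say so. The general statement in 12.1 is not exhaustive, since QoC is an exception to it, and its sentence on study-specific data does not say who takes them. The CRF, a separate attachment, may say. This stands as a limit on certainty. It does not remove the need for the plan to name the collector.
- **The direction is not established.** A reader might infer that the bias must favour PEBRA. That is the more likely direction, but intervention PEs repeatedly invite participants to share how they are doing (4.3.5), and trust in a peer could make disclosure more honest.
- **Control PEs are not strangers.** They screen, obtain consent and conduct the baseline interview, and all Sentebale PEs are trained with a focus on psychosocial support (4.3.4, 4.3.7, 13.1). Some socially desirable answering will occur in both arms. Only the excess in one arm biases the comparison.
- **The size rests on an assumption.** Nothing in the documents supports 10 points or any other value. At 3 points the effect is small.
- **Cross-checks exist.** Viral load and pill count help in judging self-reported adherence. They do not correct it, and they say nothing about QoL.
- **An external collector does not blind participants.** They still know what care they received, so the bias would be reduced and not removed.

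**Conclusion.** The point holds in this form. The plan protects follow-up QoC from collection by the PE, leaves the collector for adherence and QoL unnamed, and elsewhere makes the PE the default. Followed as written, it leaves an arm-dependent reporting risk for the three self-reported adherence items and the QoL questionnaire.

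Its size is unknown. Under the stated assumptions the false rejection rate runs from about 7% (3 points) through 10–11% (5 points) and 25–31% (10 points) to 49–63% (15 points). These figures illustrate sensitivity and do not estimate the actual bias.

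A reader might infer that all adherence results are compromised, or that the trial's main conclusion is. The documents support neither: pill count is not self-report, and the primary endpoint rests on laboratory viral load and care records. The change is worth making before data collection, but the validity of the primary analysis does not depend on it.

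**What to change.** 1. In 5.2a and 5.2b, state that the external data collector already used for QoC at 6 and 12 months also administers the three self-report adherence questions and the WHOQOL-HIV BREF, in both arms. In 12.1, say where this collector's answers are entered, which is not stated for QoC either.
2. Label any patient-reported result collected by the PE as supportive. This includes 3-month adherence. Table 1 also lists QoL and QoC at 3 months, whereas 5.2 does not; the two should be reconciled and the collector named for whatever is kept.
3. Name who performs the pill count. It need not move to the external collector, because the documents do not say whether that contact is in person.
4. Report the remaining open-label reporting bias as a limitation.

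**Cost.** The interview grows from 12 items to 12 + 31 + 3 = 46 at each of two time points, so collector time and participant burden rise. No new assessor role is needed, provided that the QoC contact can carry the added questions; the documents do not describe that contact. If it cannot, the minimum is to name the collector at each time point, justify the difference from QoC and state the limitation.

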11.2.2 Baseline characteristics; secondary, exploratory, subgroup and sensitivity analyses

Baseline characteristics will be presented according to randomized groups, no formal testing will be performed. Categorical variables will be described as absolute and relative frequencies and continuous variables as medians and interquartile ranges. As with the primary analysis, secondary (binary and categorical) endpoints will primarily be analyzed with multi-level logistic regression models and presented as odds ratios and their respective 95% CI. To estimate incidence of attrition (defaulting from care), a poisson regression will be used. We will do a quadrature check of the model fit and if found to be unreliable, we will utilize generalized estimating equations. The effect of sociodemographic and clinical determinants (age groups, gender, employment status, WHO-stage, CD4-count, HIV/ART history, HIV/AIDS knowledge, HIV/AIDS stigma) on key study outcomes will be assessed by including interaction terms in the model. If the interaction term is found to be significant, effect estimates will be summarized descriptively by subgroup. As the study is not powered for these pre-planned subgroup analyses, these results will be considered exploratory.

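### Mortality in 5.2 g) counts known deaths over all enrolled, so it is a minimum that falls as loss to follow-up rises, and no bound is planned for it

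*Combined protocol and SAP*

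**What the plan says.** Section 5.2 g) gives the endpoint as "All-cause mortality at 6 and 12 months, defined as the proportion of participants dead 6 months" and 12 months "after enrolment, respectively, out of all participants enrolled". Section 5.2 h) classes a participant as LTFU when the person, or the treatment buddy, was "more than 2 months late for a scheduled consultation or medication pick-up and no information was found about the participant". It uses the same all-enrolled denominator and the same time windows.

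On ascertainment, 5.2 g) adds "Verbal autopsy to capture cause of death whenever possible. No death certificate or autopsy report required". Section 12.1 states "Data for the follow-up period comes from routinely collected medical records at the health facilities". Section 5.1 says that "no tracking will be performed by the study staff to obtain VLs". No passage describes a search for the vital status of people who stop attending.

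On analysis, section 11.2.2 says that "secondary (binary and categorical) endpoints will primarily be analyzed with multi-level logistic regression models". Section 11.2 evaluates all participants by cluster assignment and leaves detail to a separate analysis plan. Sections 11.2 to 11.2.2 contain no rule for unknown vital status, no censoring and no sensitivity analysis for mortality.

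**The concern.** Read together, endpoints g) and h) leave a lost participant no way of being counted as dead. A death that the study learns of is a death. A death that it does not learn of sits in the LTFU group and still adds one to the mortality denominator. The proportion is thus a lower bound on mortality in each arm.

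The comparison between arms suffers if the arms lose different numbers of people, and such a difference is foreseeable. LTFU and engagement in care are themselves compared between arms, and regular contact with the peer educator is part of the intervention. If that contact retains more people, the control arm has more unknowns scored as alive, and the intervention is at a disadvantage on mortality because it kept people in view.

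**Working it through.** The plan gives no figure for expected mortality or loss, so there is nothing of its own to reproduce here. The only design figure used is the sample size in 11.1: 300 participants in 20 clusters, 10 per arm, hence about 150 per arm.

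**Formula.** Let L be the share lost in an arm, f the death risk among those with known status and u the death risk among the lost.

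- True mortality = (1 − L)·f + L·u
- Recorded mortality under 5.2 g) = (1 − L)·f
- Shortfall = L·u, which is zero or positive and never negative

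**Illustration (all rates assumed).** L = 20% control and 10% intervention; f = 1% and u = 1%, 5%, 10% or 20%, the same in both arms.

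Recorded: control 0.80 × 1% = 0.8%; intervention 0.90 × 1% = 0.9%; risk ratio 0.9/0.8 = 1.125, whatever u is.

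| u | True control | True intervention | True risk ratio |
|---|---|---|---|
| 1% | 0.8 + 0.2 = 1.0% | 0.9 + 0.1 = 1.0% | 1.00 |
| 5% | 0.8 + 1.0 = 1.8% | 0.9 + 0.5 = 1.4% | 0.78 |
| 10% | 0.8 + 2.0 = 2.8% | 0.9 + 1.0 = 1.9% | 0.68 |
| 20% | 0.8 + 4.0 = 4.8% | 0.9 + 2.0 = 2.9% | 0.60 |

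The first row shows that the lost need not die more often than the others for the recorded ratio to be off.

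**A second set of assumed rates.** L = 15% versus 5%, f = 2%, u three times that (6%). True: 1.7 + 0.9 = 2.6% versus 1.9 + 0.3 = 2.2%, odds ratio 0.84. Recorded: 1.7% versus 1.9%, odds ratio 1.12.

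**Equal loss.** L = 10% in both arms, f = 2%, u = 6%: true 1.8 + 0.6 = 2.4% in both, recorded 1.8% in both, odds ratio 1.00 either way. The level is too low but the comparison is intact, provided u is also equal.

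**Counts.** With 150 per arm, the first illustration gives 150 × 0.8% = 1.2 and 150 × 0.9% = 1.35 expected recorded deaths, against 30 and 15 people lost.

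**What bounds would show.** In the first illustration, taking 0% to 20% of the lost as dead gives 0.8% to 4.8% in control and 0.9% to 2.9% in intervention. Varied separately by arm, the risk ratio runs from 0.9/4.8 = 0.19 to 2.9/0.8 = 3.6. Death-or-LTFU is 20.8% versus 10.9%.

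**What censoring would show.** Censoring the lost at the last date known alive estimates mortality as if they then faced the risk of those still followed. Here that is about 1% in both arms and a ratio near 1.0. The false reversal goes, but where u is 5% to 20% the true levels (1.4% to 4.8%) and ratios (0.78 to 0.60) are not recovered.

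**The case against.** Several points on the other side are sound.

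- **Combined outcomes exist.** Engagement in care at 6 and 12 months (5.2 d and f) counts death, LTFU and known defaulting as failure over all enrolled. The primary endpoint also treats death and loss as failure. A reader might infer that the plan has no outcome that avoids rewarding loss; that is wrong. What is missing is a bound or adjustment for mortality itself.
- **The parts are reported.** Endpoints g) and h) share a denominator and time points and do not overlap, so a reader can add them or build a range. That stands, but the regression comparison and the range are better fixed beforehand than put together after the results are known.
- **Ascertainment is not absent.** LTFU requires that no information was found, which implies some enquiry. No certificate is needed for a death, and death is a serious adverse event that study personnel must report within 72 hours of learning of it (12.4). Each cluster, control included, has a trained peer educator (4.3.4), and the bar on tracking concerns only viral load results. This shrinks the unknown group but does not empty it.
- **Coding as survivors is inferred.** For the reported proportion it follows from the definitions. For the logistic model, one might infer that every lost participant is entered as a non-death; the text gives no rule for unknown outcomes and defers detail to a plan that is not in the documents, so that cannot be asserted.
- **The reversal is built from assumed rates** and about one recorded death per arm. No coding would support a directional conclusion at that count.

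**Conclusion.** The point holds in limited form. Under the stated definitions the mortality proportion is a minimum, too low by the share lost times the death risk among the lost, and nothing in sections 11.2 to 11.2.2 bounds or corrects it. If loss differs by arm and the death risks among the followed and among the lost are each similar across arms, the comparison is biased against the arm that retains more people. If both loss and those risks are equal, only the level is wrong. If the risk among the lost differs by arm, the ratio can be distorted even with equal loss, in either direction.

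A reader might infer that this trial's mortality result will be reversed. The documents do not support that: they give no loss or mortality rates, so the risk ratio of 1.125 against 0.78 to 0.60 shows what could happen, not what is expected. Deaths will probably be few. Severity is minor: one rare-event secondary endpoint is affected, and the primary endpoint is not, because lost participants count there as failures.

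**What to change.** In 5.2 g) and 11.2.2, and in the separate analysis plan:

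1. Label known deaths over all enrolled as minimum mortality, and show the number with unknown vital status beside it, by arm and time point.
2. Prespecify death-or-LTFU, analysed with the same multilevel logistic model. It differs from engagement in care in leaving out known defaulters. It will mostly reflect loss and should be described so.
3. Prespecify a sensitivity range that takes 0% to 20% of the lost as dead, varied separately by arm. The upper limit is a judgement and should be stated as one.
4. Optionally add time to death, censored at the last date known alive, as a supportive analysis. State that it assumes loss is uninformative and so cannot replace the range.

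The cost is wording. Mortality and LTFU are already collected on the same denominator, and the refill and dispensing records needed for step 4 are among the sources in 12.1. No extra visits or participants are needed. The downside is a wider and less tidy mortality statement.
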